3 or 4	Magnesium sulfate 6 to 10 g IV twice weekly, dependent on the patient. An initial strategy of IV replacement and every-other-day serum magnesium monitoring is helpful to guide the frequency of replacement until a steady state is reached. In a patient with normal renal function, start amiloride 5 mg PO daily and titrate up to 10 mg PO daily. Afatinib may be continued. Cetuximab should be held until recovery to Grade 2 or less. Upon recovery, resume cetuximab at next reduced dose level (afatinib dose does not need to be reduced). If \geq Grade 3 hypomagnesemia does not resolve to \leq Grade 2 within 28 days of stopping cetuximab and despite optimal supportive care, discontinue cetuximab.

e. Diarrhea

Close monitoring and proactive management of diarrhea is essential for successful treatment of patients with afatinib with or without cetuximab. Early and appropriate intervention can prevent the development of more severe diarrhea. In most cases, loperamide controls diarrhea caused by afatinib. Loperamide should be available at the start of therapy and kept with the patient at all times; it is therefore advisable that patients be given a prescription at the time of initiating

treatment with afatinib. Patients should be instructed to take two 2 mg loperamide tablets after the first episode of diarrhea, followed by one 2 mg tablet with every loose bowel movement, up to a maximum daily dose of 10 tablets (20 mg). In patients who have persistent diarrhea despite loperamide, a step-wise increase in anti-diarrheal therapy should be employed. Diphenoxylate/atropine (Lomotil) can be added (recommended dose of two 5 mg tablets up to 4 times daily, for a maximum daily dose of 20 mg) as can tincture of opium (recommended dose of 6 mg [or 10 mg/mL] up to 4 times daily, for a maximum daily dose of 24 mg [or 40 mg/mL]).

Toxicity Grade	Modification
1	Two 2 mg loperamide tablets should be taken immediately, followed by one 2 mg tablet with every loose bowel movement, up to a maximum daily dose of 10 tablets (20 mg). Add other anti-diarrheal agents as described above if necessary.
2	As with Grade 1, and appropriate rehydration (1.5 L/m ² /day plus equivalent of actual fluid loss) and electrolyte replacement.

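### Section 8.3e states the tincture of opium dose and daily maximum partly as concentrations (mg/mL), which cannot be either and do not match the mg figures beside them

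*Combined protocol and SAP*

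**What the plan says.** Section 8.3e (Diarrhea) covers afatinib with or without cetuximab, so it applies to both arms. Loperamide comes first. If diarrhea persists, two further agents may be added: diphenoxylate/atropine and tincture of opium.

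The tincture of opium single dose, frequency and ceiling are given together as a "recommended dose of 6 mg [or 10 mg/mL] up to 4 times daily, for a maximum daily dose of 24 mg [or 40 mg/mL"]. No volume is printed, and 10 mg/mL is not described as the strength of a product.

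The grade table below this text has no tincture of opium figures of its own. The Grade 1 row refers back to the agents described above it, the Grade 2 row builds on Grade 1, and the rows for prolonged Grade 2 and for Grade 3 or 4 refer to Grade 2 management. Every row therefore leads back to this one instruction.

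**The concern.** A dose and a daily maximum are amounts; mg/mL is a concentration. The bracketed entries are introduced by the word *or*, which presents them as another way of writing the mg figures, and they are not that. Both brackets carry the same unit, so a single stray character is an unlikely explanation.

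The drug is an opioid, and this is the only place in the documents that says how to give it. A prescriber or pharmacist who looks to the bracket for help in measuring a liquid finds a number that cannot be used as written. Turning it into a dose requires a guess at what was meant. The same section also makes stopping protocol treatment for diarrhea depend on non-resolution despite optimal supportive care, which is a further reason for the supportive-care text to be readable in only one way.

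**Working it through.** **Inputs, all from Section 8.3e**

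- Single dose: 6 mg, with 10 mg/mL in brackets.
- Frequency: up to 4 times daily.
- Daily maximum: 24 mg, with 40 mg/mL in brackets.

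**Step 1. Reproduce the stated maxima** (single entry × 4)

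- Unbracketed: 6 mg × 4 = 24 mg, as printed.
- Bracketed: 10 × 4 = 40, as printed.

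Both multiplications are right. The problem is the unit and the claimed equivalence.

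**Step 2. Read 10 mg/mL as a product strength**

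Under this assumption, volume = amount ÷ strength:

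- 6 mg ÷ 10 mg/mL = 0.6 mL per dose.
- 24 mg ÷ 10 mg/mL = 2.4 mL per day.

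Neither volume appears in the protocol. A strength is also a property of the bottle and stays the same however many doses are taken, so the second bracket would again have to read 10 mg/mL. It reads 40 mg/mL. The strength reading explains the first bracket at most.

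**Step 3. Read the brackets as amounts in mg**

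The fourfold step from 10 to 40 mirrors the step from 6 to 24, which suggests that the bracketed number was multiplied as if it were an amount. Compared on that footing:

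| | Unbracketed | Bracket read as mg | Ratio | Excess |
|---|---|---|---|---|
| Single dose | 6 mg | 10 mg | 10/6 = 1.67 | +67% |
| Daily maximum | 24 mg | 40 mg | 40/24 = 1.67 | +67% (40 − 24 = 16 mg/day) |

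Read this way, the two series disagree by the same factor at both points.

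**Step 4. Look for a resolution elsewhere**

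The grade table only refers back to this text. No other section gives a strength, a volume or a second statement of the dose. Neither reading makes the two brackets equivalent to the figures they follow.

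**The case against.** The strongest reply is that a complete instruction in milligrams is already printed: 6 mg, up to four times daily, to a ceiling of 24 mg. A reader might infer that the protocol gives no usable cap, or that it authorizes two doses and two ceilings. The text does not support either reading. A cap in mg stands in the same phrase, and only one of the two pairs is in dose units. The second pair becomes a dose only if the reader changes its unit.

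For the same reason, a reader might infer that the protocol directs an opioid dose 67% too high. It does not. The 67% describes one possible misreading, and the volumes in the working rest on an assumed strength that the protocol never states.

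A reader might also take the Phase Ib/II diarrhea counts in Section 2.0 (71 of 100 patients at any grade, 7 at Grade 3 or above) as the number exposed. They do not measure that. They come from patients already resistant to a tyrosine kinase inhibitor and treated with the combination, and Section 2.0 says it is unknown whether first-line toxicity will be similar. Section 8.3e adds that loperamide controls most afatinib diarrhea, and tincture of opium is one of two optional agents after that.

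Finally, the instruction is permissive, a pharmacist may well query it, and the Section 18.0 contents page is marked closed effective 04/23/2018, so a correction helps only patients still on treatment. These points stand and limit the likely harm. They do not make the brackets meaningful. The afatinib safety list in Section 3.1 is dated June 2020, so the document was still being revised after that closure date.

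**Conclusion.** The point holds as a units error in an operative supportive-care instruction. The bracketed mg/mL entries cannot be a dose or a daily maximum, no single reading explains both, and nothing else in the documents resolves them.

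- **Certain from the text:** the unit is wrong for what it labels, and the brackets are not equivalent to the mg figures.
- **Conditional:** the excess is 67% (10 against 6 mg; 40 against 24 mg) only if the brackets are misread as milligrams. The volumes of 0.6 mL and 2.4 mL hold only if 10 mg/mL is assumed to be the product strength.
- **Unknown:** how many patients in either arm would receive the drug.

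The agreement of 6 mg with 24 mg shows that this series is consistent with itself. It does not show which figures were intended, and this review takes no position on that. No endpoint or analysis is involved; sample size, power and alpha are untouched. The correction is worth making because it is cheap and concerns an opioid instruction to which every diarrhea grade leads back.

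**What to change.** The sponsor, with pharmacist confirmation, should reconcile the bracketed and unbracketed tincture of opium figures in Section 8.3e. The corrected text should state the single dose once and the daily maximum once, each as an amount. Any product strength should be labelled as a strength, and any volume should be given in mL and matched to that strength. No value is proposed here.

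The diphenoxylate/atropine figures in the same sentence can be corrected at the same time: two 5 mg tablets up to four times daily is 2 × 5 × 4 = 40 mg, against a printed maximum of 20 mg. Those figures must be reconciled too, again without this review saying which is right.

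The cost is a revision of one sentence and a notice to sites with patients still on treatment. No data collection, analysis or design parameter changes.

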8.5 Adverse Event Reporting

Toxicities (including suspected reactions) that meet the expedited reporting criteria as outlined in [Section 16.0](#) of the protocol must be reported to the Operations Office, Study Chair and NCI via CTEP-AERS, and to the IRB per local IRB requirements.

9.0 STUDY CALENDAR

9.1 STUDY CALENDAR – ARM 1: AFATINIB PLUS CETUXIMAB

REQUIRED STUDIES \ddagger	PRE STUDY	Σ																Ω	%
		Cycle 1				Cycle 2				Cycle 3				Cycle 4					
		W	W	W	W	W	W	W	W	W	W	W	W	W	W	W	W		
		1	2	3	4	5	6	7 α	8	9	10	11 α	12	13	14	15 α	16		
PHYSICAL																			
History and Physical Exam β	X	X				X				X				X				X	
Weight and Performance Status	X	X	X	X	X	X		X		X		X		X		X		X	X
Disease Assessment	X								X									X	
Toxicity Notation		X	X	X	X	X	X		X	X	X		X	X		X		X	X
Vital Signs ?	X		X		X		X		X	X	X		X	X		X			
LABORATORY																			
CBC/Differential/Platelets	X	X	X	X	X	X		X		X		X		X		X		X	X
Serum Sodium, Potassium and Magnesium	X	X	X	X	X	X		X		X		X		X		X		X	X
Serum creatinine/ Calculated creatinine clearance	X	X	X	X	X	X		X		X		X		X		X		X	X
Albumin	X	X	X	X	X	X		X		X		X		X		X		X	X
Total protein	X	X	X	X	X	X		X		X		X		X		X		X	X
Serum bilirubin	X	X	X	X	X	X		X		X		X		X		X		X	X
Alkaline phosphatase	X	X	X	X	X	X		X		X		X		X		X		X	X
AST and ALT	X	X	X	X	X	X		X		X		X		X		X		X	X
INR δ		X	X	X	X	X		X		X		X		X		X		X	X
SPECIMEN SUBMISSION																			
Tissue for banking & correlative studies \ddagger	X																	X \ddagger	
Blood, Buffy coat, & Plasma \ddagger	X								X									X	

Calendar continues on next page. Click here for [Footnotes](#)

REQUIRED STUDIES ^ã	PRE STUDY	Cycle 1								Cycle 2								Cycle 3								Ω F/U Prior to Prog	% F/U After Prog		
		W	W	W	W	W	W	W	W	W	W	W	W	W	W	W	W	W	W	W	W	W	W	W	W				
		1	2	3	4	5	6	7 ^α	8	9	10	11 ^α	12	13	14	15 ^α	16	W	W	W	W	W	W	W	W				
X-RAYS AND SCANS																													
PET scan [¿]		X																											
CT of chest and abdomen		X																X											X
Brain CT or MRI		X																X◊											X◊
ECHO or MUGA [§]		X																											
ECG [§]		X																											
TREATMENT																													
Afatinib			X	X	X	X	X	X	X	X	X	X	X	X	X	X	X	X	X	X	X	X	X	X	X	X			
Cetuximab [¶]		X		X		X		X		X		X		X		X		X		X		X		X		X			

Footnotes for Calendar 9.1:

- Σ Protocol treatment and physical, laboratory, and scan parameters will continue at the intervals indicated in the Cycle 3 and 4 columns until progression of disease or until patient has met any of the guidelines in [Section 7.6](#).
- £ Required specimen submission for patients. See [Section 15.2-15.4](#) for additional information.
- δ Only if patient is on warfarin.
- α This visit is only required for patients on cetuximab.
- β Physical exam to include cardiopulmonary examination, examination of abdomen and regional lymph nodes, and assessment of mental and neurological status.
- Ω After off treatment prior to disease progression, scans for disease assessment and physical assessments (with lab tests performed at the discretion of the treating investigator) should take place every 8 weeks until progression.
- % After off treatment following disease progression, physical assessments (with lab tests performed at the discretion of the treating investigator) should take place every 6 months for three years from the time of registration.
- ¥ If institution is participating in repeat biopsy substudy. See [Section 15.5](#) and [15.6](#).
- ◊ Only if patient has brain metastases at baseline.
- § Only if clinically indicated.
- ¶ Diphenhydramine must be given prior to first dose of cetuximab and is recommended prior to subsequent doses (see [Section 7.1](#)).
- ? Vital signs should be checked prior to each cetuximab administration, midway through the infusion, at the completion of the infusion, and one hour post the infusion.
- ã See “Best Practices for SWOG Studies” at the following URL for acceptable time windows for procedures and assessments:
<https://www.swog.org/sites/default/files/docs/2017-10/Best%20Practices%20upddate.pdf>.
- ¿ PET scans are recommended as a complement to other scans (see [Section 10.2d](#)). They are not required.

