9.2 STUDY CALENDAR – ARM 2: AFATINIB ALONE

REQUIRED STUDIES ^ã	PRE STUDY	Σ																Ω	%		
		Cycle 1				Cycle 2				Cycle 3				Cycle 4							
		W	W	W	W	W	W	W	W	W	W	W	W	W	W	W	W				
PHYSICAL																					
History and Physical Exam ^β	X	X				X				X				X				X			
Weight and Performance Status	X	X	X	X	X	X				X				X				X	X		
Disease Assessment	X									X								X			
Toxicity Notation		X	X	X	X	X				X				X				X	X		
LABORATORY																					
CBC/Differential/Platelets	X	X	X	X	X	X				X				X				X	X		
Serum Sodium and Potassium	X	X	X	X	X	X				X				X				X	X		
Serum Creatinine/ Calculated Creatinine Clearance	X	X	X	X	X	X				X				X				X	X		
Albumin	X	X	X	X	X	X				X				X				X	X		
Total Protein	X	X	X	X	X	X				X				X				X	X		
Serum Bilirubin	X	X	X	X	X	X				X				X				X	X		
Alkaline Phosphatase	X	X	X	X	X	X				X				X				X	X		
AST and ALT	X	X	X	X	X	X				X				X				X	X		
INR ^δ	X	X	X	X	X	X				X				X				X	X		
SPECIMEN SUBMISSION																					
Tissue for banking & correlative studies [£]	X																	X [¥]			
Blood, Buffy coat, & Plasma [£]	X									X								X			

Calendar continues on next page. Click here for [Footnotes](#).

REQUIRED STUDIES ^ã	PRE STUDY	Σ																Ω	%
		Cycle 1				Cycle 2				Cycle 3				Cycle 4				F/U Prior to Prog	F/U After Prog
		W	W	W	W	W	W	W	W	W	W	W	W	W	W	W	W		
X-RAYS AND SCANS																			
PET scan [¿]	X																		
CT of chest and abdomen	X									X								X	
Brain CT or MRI	X								X◊									X◊	
ECHO or MUGA [§]	X																		
ECG [§]	X																		
TREATMENT																			
Afatinib		X	X	X	X	X	X	X	X	X	X	X	X	X	X	X	X		

Footnotes for Calendar 9.2:

- Σ Protocol treatment and physical, laboratory, and scan parameters will continue at the intervals indicated in the Cycle 3 and 4 columns until progression of disease or until patient has met any of the guidelines in [Section 7.6](#).
- £ Required specimen submission for patients. See [Section 15.2-15.4](#) for additional information.
- δ Only if patient is on warfarin.
- β Physical exam to include cardiopulmonary examination, examination of abdomen and regional lymph nodes, and assessment of mental and neurological status.
- Ω After off treatment prior to disease progression, scans for disease assessment and physical assessments (with lab tests performed at the discretion of the treating investigator) should take place every 8 weeks until progression.

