The primary objective for the new design is to compare PFS between the arms at the 1-sided 0.025 level. This analysis would take place when 134 PFS events or 70% of the events among eligible patients have been observed (whichever comes first and will depend on sample size attained). With 134 PFS events, this study has 90% power to detect a hazard ratio of 0.57 (75% improvement). The following table describes the analysis as a function of how many patients are accrued by the time of study closure:

Final Sample Size	# events at analysis	HR with 90% power	improvement in PFS
160	112	0.54	85%
180	126	0.56	78%
200	134	0.57	75%
212	134	0.57	75%

An interim analysis will take place when 64 PFS events have been observed. This analysis will be presented to the SWOG Data and Safety Monitoring Committee at the SWOG Group Meeting closest to this number of events. This analysis will evaluate if there is evidence to recommend early stopping of the study for futility by testing the null hypothesis at the 0.5 level, using a stratified log-rank test. If the p-value is 0.5 or greater, than the recommendation will be that there is insufficient evidence to continue accrual to this study.

Secondary Objectives under the revised design are to compare response rates, OS, time to treatment failure (TTF), time to treatment discontinuation (TTD), and toxicity.

Assuming 212 patients enrolled over 36 months with 14 months of additional follow-up, a one-sided log-rank test with an alpha of 0.025 has 90% power to detect an OS hazard ratio of 0.5, corresponding to a 2-fold increase in median OS, under the exponential distribution. Similarly, if it is assumed that the median TTF is 11 months, and the median TTD is also 11 months, there will be 92% power to detect a 70% increase in medians (hazard ratio of 0.59) for each of these endpoints.

Assuming 85% of patients will have measurable disease, 180 patients will be evaluable for the response comparison between arms. Response rates between the arms will be compared using a chi-squared test of independence at the 1-sided 5% level. With 90 patients per arm, this design has 93% power to detect at least a 22% difference in response rates between the arms and within each arm the rates can be estimated to within 10% with 95% confidence.

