Toxicity rates between arms will be assessed using a chi-squared or Fisher's exact test (as appropriate) at the 1-sided 5% level. Assuming all eligible patients are evaluable for toxicities, rates can be estimated to within 10% with 95% confidence and any toxicity with at least 5% prevalence has almost a 100% chance of being observed. With 106 patients per arm, this design has 92% power to detect at least a 20% difference between the arms.

d. Secondary Objectives

Additional analyses will be to compare response rates, OS, time to treatment failure (TTF), time to treatment discontinuation (TTD), and toxicity.

Assuming 212 patients enrolled over 36 months with 14 months of additional follow-up, a one-sided log-rank test with an alpha of 0.025 has 90% power to detect a OS hazard ratio of 0.5, corresponding to a 2-fold increase in median OS, under the exponential distribution. Similarly, if it is assumed that the median TTF is 11 months, and the median TTD is also 11 months, there will be 92% power to detect a 70% increase in medians (hazard ratio of 0.59) for each of these endpoints.

Assuming 85% of patients will have measurable disease, 180 patients will be evaluable for the response comparison between arms. Response rates between the arms will be compared using a chi-squared test of independence at the 1-sided 5% level. With 90 patients per arm, this design has 93% power to detect at least a 22% difference in response rates between the arms and within each arm the rates can be estimated to within 10% with 95% confidence.

Toxicity rates between arms will be assessed using a chi-squared or Fisher's exact test (as appropriate) at the 1-sided 5% level. Assuming all eligible patients are evaluable for toxicities, rates can be estimated to within 10% with 95% confidence and any toxicity with at least 5% prevalence has almost a 100% chance of being observed. With 106 patients per arm, this design has 92% power to detect at least a 20% difference between the arms.

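### From cycle 2 the shared laboratory tests are drawn every 2 weeks in Arm 1 but every 4 weeks in Arm 2, so the toxicity test in 11.2 can show an Arm 1 excess of short-lived laboratory events that comes from the visit schedule

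*Combined protocol and SAP*

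**What the plan says.** **Calendars.** In 9.1 (Arm 1) the blood count, electrolyte, creatinine, albumin, total protein, bilirubin, alkaline phosphatase and AST/ALT rows are marked at weeks 1 to 5 and then at weeks 7, 9, 11, 13 and 15. In 9.2 (Arm 2) the same rows are marked at weeks 1 to 5 and then at weeks 9 and 13 only. Weeks 7, 11 and 15 in Arm 1 carry the footnote "This visit is only required for patients on cetuximab". A footnote in both calendars extends the pattern: "laboratory, and scan parameters will continue at the intervals indicated in the Cycle 3 and 4 columns until progression of disease", or until a criterion for removal from treatment is met.

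**Analysis.** Toxicity is a planned between-arm comparison: "Secondary Objectives under the revised design are to compare response rates, OS, time to treatment failure (TTF), time to treatment discontinuation (TTD), and toxicity". The method in 11.2 is "Toxicity rates between arms will be assessed using a chi-squared or Fisher's exact test (as appropriate) at the 1-sided 5% level", with the design statement "With 106 patients per arm, this design has 92% power to detect at least a 20% difference between the arms". Section 11.2 does not restrict laboratory events to visits that both arms share, adjust for the number of draws, or set laboratory events apart.

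**The concern.** A patient can report a symptom at the next visit. A laboratory abnormality that appears and resolves between two draws is recorded only if blood is taken while it is present. If the arms have the same true rate of such events but one is sampled twice as often, that arm records up to twice as many.

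The direction is known in advance and runs against the combination. The nominal 5% level gives no protection, because the bias is in what is recorded and not in the test. At stake is how an Arm 1 excess in transaminases, potassium, creatinine or counts would be read in the safety comparison.

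**Working it through.** **Inputs from the documents.** 106 patients per arm, 1-sided 5%, 20-point difference and 92% power (11.2); draw weeks (9.1, 9.2); median time to treatment discontinuation of 11 months, assumed in 11.2. **Inputs not in the documents.** The true rate of transient laboratory events and their duration D; both are assumed and shown as ranges.

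**1. The plan's own figure.** The baseline rate is not given. At 25% vs 45%, z = (0.20 − 1.645 × √(2 × 0.35 × 0.65/106)) / √((0.25 × 0.75 + 0.45 × 0.55)/106) = (0.20 − 0.1078)/0.0641 = 1.44, a power of 92.5%. At 30% vs 50% it is 91.2%, and at 40% vs 60% it is 90.2%. The stated 92% is reproduced for baselines near 25-30%.

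**2. Number of scheduled draws.** Four cycles: 4 + 2 × 3 = 10 in Arm 1 and 4 + 3 = 7 in Arm 2. Eleven months is about 12 cycles of 28 days: 4 + 2 × 11 = 26 against 4 + 11 = 15, for a patient who stays on cetuximab.

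**3. Events after cycle 1 only.** For an abnormality of D days starting at a random time, the recorded rate is the true rate × min(1, D/14) in Arm 1 and × min(1, D/28) in Arm 2. The chance that the 1-sided 5% test at 106 per arm declares an Arm 1 excess, by exact enumeration of the two binomials, is:

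| True rate, both arms | D (days) | Recorded, Arm 1 vs Arm 2 | Chi-squared | Fisher |
|---|---|---|---|---|
| 20% | 7 | 10% vs 5% | 41% | 30% |
| 20% | 14 | 20% vs 10% | 66% | 60% |
| 20% | 21 | 20% vs 15% | 25% | 20% |
| 20% | 28 | 20% vs 20% | 5% | 4% |
| 10% | 7 | 5% vs 2.5% | 27% | 13% |
| 10% | 14 | 10% vs 5% | 41% | 30% |
| 10% | 21 | 10% vs 7.5% | 16% | 11% |
| 5% | 7 | 2.5% vs 1.25% | 18% | 4% |
| 5% | 14 | 5% vs 2.5% | 27% | 13% |
| 5% | 21 | 5% vs 3.75% | 13% | 5% |

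**4. Counting cycle 1 as well.** Take events at a constant weekly rate λ over 12 cycles, with λ = −ln(1 − 0.20)/48 for a 20% cumulative incidence and D now in weeks. Expected detections are λ × (4 × min(1, D) + 44 × min(1, D/2)) in Arm 1 and λ × (4 × min(1, D) + 44 × min(1, D/4)) in Arm 2. For D = 2 this is 48λ against 26λ, so recorded rates are 20.0% and 1 − 0.8^(26/48) = 11.4%. The false-positive rate is 54% (chi-squared) or 47% (Fisher). For D = 1 it is 33% or 25% and for D = 3 it is 20% or 16%. For D of 4 weeks or more it is 5% or 4%.

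**5. Counting common draws only.** If finding an abnormality does not change its course, detection is equal and the chi-squared rate returns to about 5-6%. That condition may fail. Section 8.3j holds all protocol treatment for Grade 2-4 transaminases. Suppose the true rate is 20% in both arms, an unmanaged abnormality lasts at least 28 days, and it resolves within 14 days of a hold. Half of the Arm 1 abnormalities start before the mid-cycle draw, are found there and have resolved by the next common draw, so 20% × 1/2 = 10% is recorded in Arm 1 against 20% in Arm 2. A true 40% vs 20% would be recorded as 20% vs 20%, and the chance of detecting it falls from 94% to 5%.

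**The case against.** The strongest case on the other side has four parts.

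- **Size.** D = 14 days is where this model's gap is widest, and nothing in the documents supports abnormalities of 7-14 days. Afatinib is given daily without a break, and 8.3j allows up to 28 days for resolution after stopping, so lasting abnormalities are plausible and would show no bias. The afatinib adverse event list in 3.1 puts raised ALT, AST and creatinine and low potassium in its column of 20% or less, and lists falls in blood counts among events with insufficient evidence of causation. A 20% rate is therefore a ceiling. All of this stands.
- **Consequence.** Toxicity is a secondary comparison with no stopping or success rule tied to this test, and the focus toxicities named in the Phase II interim text are rash and diarrhea. This limits the stakes. It does not remove laboratory events from the comparison, which 11.2 leaves unrestricted.
- **Remedy.** A reader might infer that the formal test should simply be replaced by one on common draws. Step 5 shows why not: when mid-cycle findings lead to treatment holds, that test can hide real Arm 1 toxicity.
- **Data.** Section 14.4 lists adverse event forms per cycle and no dated laboratory results, so draw dates may not be to hand. Equal form frequency does not equalise the number of draws behind each form.

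A reader might also infer that losing the extra visits after cetuximab stops adds to the bias. It changes ascertainment within Arm 1, but it narrows the gap between arms.

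**Conclusion.** The schedules differ, the planned test takes no account of it, and the bias it can produce has one direction. It is confined to laboratory abnormalities that start after cycle 1, last under 4 weeks and are not picked up by unscheduled bloods.

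With equal true rates of 5-20% and 106 per arm, the chi-squared false-positive rate is about 13-66% for durations of 7-21 days and about 5% from 28 days. Including cycle 1 reduces the excess; at a 20% rate and 14 days, 66% becomes 54%. Fisher's test gives lower figures and, for the rarest events, hardly exceeds its nominal level. Rate and duration are assumptions, and unscheduled bloods and early cetuximab discontinuation would reduce every figure.

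A reader might infer that about two trials in three would show a spurious signal. The documents do not support that: 66% is the worst duration at the highest assumed rate. They support a bias that can occur, with a known direction and an unknown size. Magnesium, scheduled in Arm 1 only ("Serum Sodium, Potassium and Magnesium"), is a separate matter and is not in these figures.

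**What to change.** In the toxicity paragraph of 11.2:

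1. Keep the all-events test as it is.
2. For laboratory-graded toxicities measured in both arms, pre-specify a supporting between-arm comparison where ascertainment is equal: (a) events in cycle 1, sampled weekly in both arms and available from the per-cycle adverse event form; (b) if draw dates are available, events at the draws common to both calendars (weekly in cycle 1, then day 1 of each later cycle).
3. State that an Arm 1 excess seen only in the all-events test after cycle 1 may reflect the visit schedule.
4. State that the common-draw result can understate Arm 1 toxicity, because mid-cycle findings trigger treatment holds.

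The cost is a little more analysis work and lower precision in the supporting comparison. Part (b) may need dates collected retrospectively, since the appendix page carries a closure stamp of 23 April 2018; part (a) does not depend on draw dates. Visits, treatment rules and the primary analysis are unchanged.
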